4.5 Transitional Care Management Billing

According to CMS guidelines,³ transitional care management (TCM) requires four core components: (1) transition in care from an inpatient setting to a community setting; (2) receipt of communication from a provider (direct contact, telephone, or electronic) within 2 business days of discharge; (3) moderate or high complexity medical decision making; and (4) a face-to-face clinical visit within 7 or 14 calendar days of discharge from the inpatient setting.

The TCM billing endpoint will be defined as incidence of TCM billing with the associated estimand being the odds ratio from a logistic model. Transitional care management billing is defined as an office visit billing through Current Procedural Terminology (CPT) codes 99495 (for a visit within 14 days of index hospitalization discharge) and 99496 (for a visit within 7 days of index hospitalization discharge). Because TCM billing codes became effective under Medicare's Physician Fee Schedule, and BCBS and Medicaid may not consistently use these codes, this endpoint will be defined for FFS Medicare participants only. The 30-day TCM eligibility period begins on the beneficiary's inpatient discharge date and continues for the next 29 days. Medicare beneficiaries who die or who have a hospital readmission within 30 days following the index discharge are not eligible to have a TCM claim. Therefore, even if they received TCM core components, such patients do not meet the TCM billing criteria. Because TCM billing can be rendered by physicians and non-physician practitioners in inpatient and outpatient setting, our assessment of TCM code billing will include claims from all practitioners.

4.6 Recurrent Stroke

The recurrent stroke endpoint will be defined as the time to admission for stroke (inpatient or observation stay) to a non-federal, acute care hospital. Readmissions for stroke will be identified using the primary discharge diagnosis ICD-10 codes associated with cerebral infarction, subarachnoid hemorrhage, and intracerebral hemorrhage (**Appendix B**). The associated estimand is the hazard ratio from a recurrent time-to-event analysis. Patients will be administratively censored one year after index hospitalization discharge.

4.7 All-Cause Mortality

Deaths within 1 year of index discharge were ascertained from the North Carolina State Death Index as well as insurance claims beneficiary summary files. A death identified in either database will be considered a death.

5 CLAIMS ANALYSES

5.1 Phase 1 Intent-to-Treat Analyses

We will perform intent-to-treat analyses comparing the COMPASS intervention to UC with respect to all endpoints listed in Table 1 stratified by insurance provider (i.e., FFS Medicare, NC Medicaid (excluding patients with dual Medicare coverage), BCBS-NC). Comparisons will be made based on the intervention arm to which a patient belongs regardless of whether the patient received any intervention. For intent-to-treat analyses, all individuals must have been enrolled at the time of the index discharge event in one or more of the insurers (CMS Medicare, NC Medicaid, or BCBSNC). The FFS Medicare analysis population will include participants enrolled in CMS Medicare Parts A & B. Participants only enrolled in Part A or those enrolled in Part C (Medicare Advantage) will be excluded. The Medicaid analysis population will include participants enrolled in a qualifying Medicaid plan. Examples of non-qualifying plans include plans only covering children, plans for pregnancy-related care, cancer-related care, or those covering emergency services only. Participants dually enrolled in Medicaid and Medicare will be excluded from the Medicaid analyses. The BCBS analysis population will consist of participants enrolled in BCBS of NC, not also enrolled in Medicare.

5.2 Phase 2 Intent-to-Treat Analyses

We will perform intent-to-treat analyses comparing outcomes in Phase 2 to Phase 1 with respect to all endpoints listed in Table 1 stratified by insurance provider as described in Section 5.1. Phase 2 analyses will include an analysis of Sustainability that compares Phase 2 Sustainability to the Phase 1 Intervention phase. The analysis populations will be defined as above in Section 5.1 with the added requirement that the analysis is restricted to hospitals that were randomized to INV in Phase 1 and that delivered the COMPASS intervention per protocol to at least 1 participant in Phase 2 Sustainability. Phase 2 analyses will also include an analysis of pre-post comparative effectiveness that compares Phase 2 Intervention to Phase 1 Usual Care. This analysis is restricted to the set of hospitals that were randomized to Usual Care in Phase 1 and that delivered the COMPASS intervention to Phase 1 Usual Care in Phase 2.

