- 2) Using responses from the 90 day survey, we will measure self-rated general health; medication adherence (MMAS-4); self-monitoring of blood pressure; global disability; physical activity; depression (PHQ2); cognition (Mini MOCA); falls; fatigue; and satisfaction of care.
- 3) Using claims data from multiple payer sources up to 12 months after stroke hospitalization, we will measure effectiveness of COMPASS vs usual care for all-cause readmissions at 30 and 90 days and 1-year post-discharge.
- 4) Comparative effectiveness of the COMPASS vs usual care on: mortality; health care utilization; (emergency department visits, admissions to skilled nursing facilities/inpatient rehabilitation facilities); and use of transitional care management billing codes. We will use claims data from multiple payer sources up to 12 months after stroke hospitalization.
- 5) For all outcomes we will adjust analyses to account for race, sex, age, stroke severity, and insurance status.

Exploratory Aims:

- 1) Phase 2: The implementation sustainability objectives for Phase 2 of the COMPASS Study are to characterize whether rates of transitional care management (TCM) delivery and eCare plan delivery are sustained, worsen, or improve during the sustainability period of the COMPASS study for hospitals randomized to the intervention during Phase 1.
- 2) Phase 2: The effectiveness sustainability objective for Phase 2 of the COMPASS Study is to characterize whether patient outcomes are sustained, worsen, or improve during the sustainability period of the COMPASS study for hospitals randomized to the intervention during Phase 1.
- 3) Phase 2: The primary comparative effectiveness objective for Phase 2 of the COMPASS Study is to evaluate whether Stroke Impact Scale 16 (SIS-16) scores are improved during Phase 2 (i.e., the intervention phase) for hospitals randomized to usual care in Phase 1.
- 4) Phase 2: Using Claims, the Pre-Post analyses compared outcomes in hospitals randomized to provide UC in Phase 1 with outcomes among those that crossed over and delivered the INV in Phase 2 for mortality; health care utilization; (emergency department visits, admissions to skilled nursing facilities/inpatient rehabilitation facilities); and use of transitional care management billing codes. We will use claims data from multiple payer sources up to 12 months after stroke hospitalization.

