- 5). Phase 2: Using Claims, the Sustainability analyses compared outcomes in hospitals randomized to deliver the INV in Phase 1 with outcomes among those that sustained the intervention (SUS) in Phase 2 for mortality; health care utilization; (emergency department visits, admissions to skilled nursing facilities/inpatient rehabilitation

Application - IRB00035998

facilities); and use of transitional care management billing codes. We will use claims data from multiple payer sources up to 12 months after stroke hospitalization.

Data Collected for Ancillary Studies:

- 1) Analysis of individual, organizational, and community factors affecting implementation of COMPASS through supplemental funding (CTSI Award lead by Co-I [name]). This pilot project will contribute to a process evaluation of our Phase1, intervention-randomized health systems adopting COMPASS.
- 2) An exploratory analysis that compares patient clinic return rate and use of services to physical locations of patients and services (i.e. distance and drive times to/from clinics and community resources).
- 3) At the 90 day survey, we will also use the PROMIS Global-10 instrument that assesses general domains of health and functioning including overall physical health, mental health, social health, pain, fatigue, and perceived quality of life. These are similar in nature to our primary outcome, the SIS-16.

Hospital Performance Metrics (to support participating sites in delivery of the intervention):

1) Evaluate compliance with the new model of post-acute stroke care by exploring quality indicators among intervention hospitals, (e.g., proportion of patients called within 2 days after hospital discharge; proportion of patients seen by an advanced practice provider [MD/NP/PA] within 7 to 14 days from hospital discharge; and proportion of eligible patients receiving home or outpatient rehabilitation therapy).

Methods and Measures

Study Design

The COMPASS Study is a pragmatic, cluster-randomized trial of 41 hospitals in North Carolina designed to determine the effectiveness of a model of post-acute stroke care (i.e. the COMPASS Intervention) compared with usual care (Control).

Study Setting

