6.1 Covariate Adjustment

Unless otherwise stated below, where feasible the following covariates will be incorporated in analysis models for all endpoints described in Table 1.

- 1. Study Arm (intervention, usual care) ITT Phase 1 analyses only
- 2. Study Phase (sustainability, intervention) ITT Phase 2 sustainability analyses only
- 3. Study Phase (intervention, usual care) ITT Phase 2 effectiveness analyses only
- 4. Race (non-white; white)
- 5. Age (degree two polynomial)
- 6. Index hospitalization diagnosis (stroke; TIA)
- 7. NIH Stroke Scale (NIHSS) Score category (0, 1-4, 5-15, and 16-42) categories may be collapsed to 5-42 due to sample size requirements.
- 8. Sex (female; male)
- 9. Prior stroke
- 10. Prior TIA

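### The Phase 2 claims comparisons are labelled intent-to-treat but are before-after contrasts in delivering hospitals, and their time-to-event intervals rest on a sandwich variance from at most about 20 hospitals with no small-sample correction stated in this SAP

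*SAP*

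**What the plan says.** SAP 5.2 opens: "We will perform intent-to-treat analyses comparing outcomes in Phase 2 to Phase 1 with respect to all endpoints listed in Table 1". It then describes two comparisons.

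- **Sustainability:** Phase 2 Sustainability against Phase 1 Intervention. For the patients, "The analysis populations will be defined as above in Section 5.1"; the hospitals are further "restricted to hospitals that were randomized to INV in Phase 1 and that delivered the COMPASS intervention per protocol to at least 1 participant", a condition judged on Phase 2 delivery.
- **Pre-post:** Phase 2 Intervention against Phase 1 Usual Care, in hospitals "randomized to Usual Care in Phase 1 and that delivered the COMPASS intervention to Phase 1 Usual Care in Phase 2".

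SAP 5.1 gives the patient-level rule: "Comparisons will be made based on the intervention arm to which a patient belongs regardless of whether the patient received any intervention". SAP 6.1 repeats the label in its covariate list, for example "Study Phase (sustainability, intervention) ITT Phase 2 sustainability analyses only".

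The protocol's Exploratory Aims 4 and 5 describe the same comparisons. Aim 4 sets Phase 1 usual-care hospitals against outcomes "with outcomes among those that crossed over and delivered the INV in Phase 2". Aim 5 "compared outcomes in hospitals randomized to deliver the INV in Phase 1 with outcomes among those that sustained the intervention (SUS) in Phase 2".

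For inference, SAP 6.3.1 and 6.3.2 plan marginal Cox models and 6.3.3 plans PWP models, all with a robust sandwich variance clustered on hospital. No small-sample adjustment or reference distribution is named. SAP 2 and 6.4 refer to the Phase 1 SAP, of which this document is an addendum; that plan was not available for this review.

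**The concern.** Intent-to-treat normally means that units are compared as randomised and that none is dropped for what it did afterwards. Here the exposure is phase, not allocation, and a hospital stays in only if it delivered in Phase 2, which is known only after randomisation. A reader who sees the label may give the phase hazard ratio the protection of randomisation, which it does not have.

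The sandwich variance relies on many clusters. With 20 or fewer it tends to be too small, and a normal quantile makes the interval narrower still. Phase 2 is exploratory and no alpha is stated, so the harm lies in interpretation: a chance difference between phases can look like evidence that the program worked, lasted or faded.

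**Working it through.** **1. Label against definition.**

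| | Protocol, Analytical Plan (ITT) | SAP 5.2 |
|---|---|---|
| Hospitals | every randomised hospital | one arm only, if it delivered in Phase 2 |
| Exposure | allocated arm | study phase |
| Patients | all discharged directly home | apparently regardless of receipt, through 5.1 |

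The first two rows do not match. The 6.1 covariates contain no calendar time, and neither comparison has a concurrent group, so any secular change goes straight into the phase effect.

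**2. Number of clusters.** The protocol gives 41 hospitals, two randomised together: 40 units, 20 per arm. Each Phase 2 comparison therefore starts from about 20, before the delivery rule. The number kept is not stated; 15 is used below as an assumption. Time-to-event endpoints: one in 6.3.1, three in 6.3.2 and two in 6.3.3, so six (four Cox, two PWP).

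**3. The plan's own figure.** There is none: no alpha, power or intracluster correlation is given for these analyses. A two-sided 95% interval is assumed.

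**4. Rough analytic check.** Suppose the estimate divided by its sandwich SE times √(G/(G−1)) follows t with G−1 df. The planned interval then covers 1 − 2·P(T > 1.96·√((G−1)/G)), which is 92.9% for G = 20 and 92.1% for G = 15.

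**5. Main simulation, no true phase effect.**

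- *From the documents:* uniform entry from 1 June 2016 to 31 March 2018 (Phase 1) and from 1 November 2017 to 31 January 2019 (Phase 2); follow-up one year or to 30 June 2019.
- *Assumed:* hospital log-SD 0.2; no hospital-by-phase variation; about 50 patients per hospital-phase, either equal or 15/50/120 in shares 45/30/25%; one-year risk 8% or 40%; PWP gamma frailty variance 0.5.
- The 8% extends the 2.0% 90-day mortality in SAP 6.2 at constant hazard: 1 − 0.98^(365/90) = 7.9%.
- 4,000 runs per setting, Monte Carlo SE about 0.4 points.

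False-positive rate, uncorrected sandwich with normal quantile:

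| Model | 20 hospitals | 15 hospitals |
|---|---|---|
| Cox | 7.8-8.4% | 8.3-10.0% |
| PWP, gap time | 6.6-8.7% | 7.9-10.2% |
| PWP, total time | 7.3-8.3% | 7.4-9.7% |

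Cox with 15 patients per hospital-phase, 40% risk and 20 hospitals gave 6.8% (equal sizes) and 8.4% (unequal). Coverage is 100% minus these rates: 91.3-93.4% at 20 hospitals (100 − 8.7 to 100 − 6.6) and 89.8-92.6% at 15 (100 − 10.2 to 100 − 7.4). The mean SE was 0.897-0.964 of the empirical SD, so about 4-10% too small.

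**6. Second Cox simulation, other assumptions.** With 50 or 10 patients per hospital-phase, size CV 0 or 0.8 and hospital-by-phase SD 0.15, coverage was 90.0-93.6% at 20 hospitals and 90.3-91.7% at 15. With that SD set to zero (20 hospitals, CV 0.8) it was 91.5%; with an 8% event rate, 91.2%.

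**7. What a correction does.** A delete-one-hospital jackknife with t on G−1 df gave 4.4-5.9% false positives in the main simulation. In the second it gave 93.7-95.5% coverage at 20 hospitals and 94.3-94.9% at 15. A t reference alone left 5.0-7.7% in the main simulation.

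**8. Why the conclusion must stay before-after.** Take no intervention effect and an assumed secular drift of HR 0.95. With SE 0.0871, m = ln(0.95)/0.0871 = −0.589, and the rejection rate is Φ(−1.96 − m) + 1 − Φ(1.96 − m) = 9.1%. With SE 0.0958 it is 8.3%. Using the smaller mean sandwich SEs (0.082 and 0.086) it becomes 11.2% and 12.1%. Correcting the variance does not remove drift.

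**The case against.** The SAP hides nothing: it calls one comparison pre-post, names the phases and states the hospital restrictions. The restriction fits Exploratory Aims 4 and 5, which ask about hospitals that delivered or sustained. Under the sustainability rule a single participant is enough, and a hospital with no Phase 2 patients has no Phase 2 data under any rule. The intent of the pre-post sentence can be recovered from Aim 4. The undercoverage is moderate and rests on assumed sizes and heterogeneity. All of this stands, and it narrows the point. It does not make the label right or supply a small-sample method.

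Four stronger readings are tempting and are not supported:

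- *That patients who received nothing are dropped.* The sustainability paragraph carries over the 5.1 populations, and 5.1 analyses patients regardless of receipt.
- *That the delivery rule biases the results.* The documents do not say that it removes any hospital, and no bias has been shown.
- *That the intervals are certainly uncorrected.* This is inferred from the silence of an addendum; the Phase 1 SAP may hold a correction.
- *That the binary endpoints share the fault.* A random-intercept logistic model as in SAP 6.2 gave 4.3-5.6% false positives in simulation when hospital risks did not vary between phases. Inflation appears only with an assumed amount of such variation, and the documents give none.

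**Conclusion.** The intent-to-treat label in SAP 5.2 and in 6.1 items 2 and 3 is wrong by the protocol's own definition. These are non-randomised before-after comparisons in delivering hospitals.

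For the six time-to-event endpoints, unless the Phase 1 SAP supplies a correction, nominal 95% intervals cover roughly 91-93% with 20 hospitals and about 90-93% with an assumed 15. The size depends on assumed hospital sizes, heterogeneity and event risks; undercoverage appeared in every setting tried. The simulations used phase as the only covariate and no imputation. Because the analyses are exploratory, the change should be made, but it does not touch the trial's primary result. The unclear pre-post sentence is a wording repair and does not carry the point.

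**What to change.** 1. Relabel SAP 5.2 and 6.1 items 2 and 3 as non-randomised before-after comparisons in delivering hospitals, with patients analysed regardless of receipt. Limit the Phase 2 conclusion to a before-after association.
2. For the Phase 2 Cox and PWP models, use a small-sample-corrected hospital sandwich, for example a delete-one-hospital jackknife, with a t reference on hospitals minus 1 df. Apply it within each of the 100 imputed datasets of SAP 6.4 and pool with a matching small-sample df. If the Phase 1 SAP already has such a rule, citing it is enough.
3. Rewrite the pre-post sentence so that it can be applied, with its delivery threshold stated as in the sustainability rule, and report how many randomised hospitals each rule removes. A sensitivity analysis in all originally randomised hospitals with Phase 2 enrolment is optional; it would not be intent-to-treat either.

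The cost is SAP wording and modest extra computation on existing data. In the main simulation the corrected intervals are about 10-15% wider at 20 hospitals and 14-21% wider at 15.

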analyses. The analyses will be performed at the individual level with adjustment for lack of independence between hospitals. The primary analysis of patient-centered outcomes will occur at the end of Phase 1.

Subjects Selection Criteria

Inclusion Criteria:

 Patients aged 18 years or older, discharged home from a participating COMPASS Study hospital with a diagnosis of ischemic or hemorrhagic stroke or transient ischemic attack (TIA).

Exclusion Criteria:

- Patients transferred to another short-term acute care hospital, skilled nursing facility, inpatient rehabilitation facility, or hospice.
- Patients with a diagnosis of subdural or aneurysmal subarachnoid hemorrhage.
- Patients who speak neither English nor Spanish.

Sample Size:

- Approximately 6,000 potentially eligible participants during Phase 1
- Approximately 6,000 potentially eligible participants during Phase 2

Intervention and Interactions

As described in the Methods section above, the trial has two Phases (see Figure 1).

- Phase 1: Patient enrollment for Phase 1 of the trial will run from June 2016 to March 2018. Phase 1 includes a control arm (Control Hospital) and an intervention arm (COMPASS-Intervention Hospitals). Details of these arms and interactions are described below. Figure 2 depicts the patient flow of activities for Phase 1 when there is a control arm and COMPASS intervention arm.
- Phase 2: Patient enrollment for Phase 2 of the trial will run from November 2017 January 2019. Phase 2 includes an intervention arm (COMPASS-Intervention hospital) and the other arm is COMPASS Hospitals who will sustain the COMPASS intervention using their own hospital resources (COMPASS-Sustain hospital). Detail of these arms and interactions are described below.
- Note, that there is some overlap between Phases 1 and 2. The overlap is due to differences in the timing of hospital recruitment and enrollment (i.e. larger hospitals enrolled patients faster).

COMPASS will support hospitals in implementing structured post-acute stroke services consistent with CMS transitional care codes and management. Hospitals which participate are implementing COMPASS as the new standard of care. The goal of COMPASS is to structure and organize the processes of post-acute care to optimize patient recovery function, reduce caregiver stress, improve risk factor management, and facilitate self-management of risk factors.

Phase 1: Patients in Control Hospitals

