6.1.1 Sensitivity to Covariate Adjustment

Where feasible, we will also perform analysis using different covariate sets that includes as possible adjustment variables the set above as well as other covariates. These additional covariates include but are not limited to:

- 1) Whether the patient lives in a rural or urban area (based on RUCA codes)
- 2) Whether the hospital is in a rural or urban area (based on RUCA codes)
- 3) Whether the patient had a rehabilitation referral at discharge (physical therapy, occupational therapy, or speech therapy)
- 4) Whether the patient had a home health referral at discharge
- 5) Whether the patient had a documented PCP in their medical record
- 6) Dual eligibility for Medicaid (FFS analyses only)
- 7) History of depression
- 8) History of hypertension
- 9) History of smoking
- 10) History of CVD comorbidities

Covariates listed above will be ascertained as part of the COMPASS study and not from claims. Variables will be selected for inclusion in the sensitivity analysis model using a backward selection procedure that accounts for missing covariate data using methods described in Section 6.5. The sensitivity model will include key clinical covariates as well as any of the above variables that have a p-value > 0.10 (unadjusted for multiple comparisons). Estimates of treatment effects will be produced for each step in the model selection procedure to understand how effect estimates change based on different adjustment sets.

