6.2 Analysis of Binary Endpoints

The set of binary endpoints to which this section pertains are given as follows:

1. Incidence of 30-day all cause readmissions

- 2. Incidence of 90-day all cause readmissions
- 3. Use of TCM billing codes

For the analysis of 30- and 90-day all cause readmissions, patients who have continuous coverage over the 30- or 90-day reference period will be included in the analysis. For analysis of TCM billing codes, patients who have continuous coverage over the 30-day period following discharge from the index hospitalization will be included in the analysis. The percentage of patients with incomplete coverage over the 90-day period following discharge from the index hospitalization is expected to be low. In the event that more than 10% of the patients linked to claims data have incomplete coverage over the relevant 30- or 90-day reference period, we will assess the robustness of any important findings to exclusion of these patients from analyses using techniques such as multiple imputation from a time-to-event model that accounts for the observed follow-up period for patients who drop out of coverages during the relevant reference period.

For readmission endpoints, patients who die prior to the end of the reference period without a qualifying readmission will be treated as not having a readmission. Prior analyses of 90-day mortality based on the full COMPASS cohort has demonstrated that the percentage of patients who die within 90 days of discharge from the index hospitalization is approximately 2.0% and did not differ by treatment arm.⁴ Thus, the impact of excluding patients who did not survive for the entire reference period is not expected to strongly influence results. Nonetheless, in the event that more than 5% of the patients linked to claims data die within the reference period, we will assess the robustness of any important findings by performing a sensitivity analyses that includes these patients as having met the endpoint for all cause readmissions.

For all binary endpoints, we will employ generalized linear mixed models (GLMM) with a logistic link function. Models will include a hospital-specific random effect, and adjust for the covariates described in Section 6.1.

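### The Phase 2 pre-post effectiveness estimate mixes the COMPASS effect with secular change, and no analysis is planned that uses the other arm to separate them

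*SAP*

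**What the plan says.** SAP Section 5.2 sets out two Phase 2 analyses of every Table 1 endpoint, stratified by insurer.

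- The pre-post comparative effectiveness analysis "compares Phase 2 Intervention to Phase 1 Usual Care". On its hospitals the SAP says: "This analysis is restricted to the set of hospitals that were randomized to Usual Care in Phase 1", with the further condition that they delivered COMPASS in Phase 2.
- The Sustainability analysis compares the two phases within the hospitals first randomized to the intervention.

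The exposure term for the pre-post model is item 3 of SAP Section 6.1: "Study Phase (intervention, usual care) ITT Phase 2 effectiveness analyses only". The remaining covariates there are race, age, index diagnosis, NIHSS category, sex, prior stroke and prior TIA. For binary endpoints, SAP Section 6.2 says: "Models will include a hospital-specific random effect, and adjust for the covariates described in Section 6.1". The time-to-event models in Section 6.3 adjust for hospital clustering through a sandwich variance. Section 6.1.1 names ten further candidates for sensitivity models, introduced by "These additional covariates include but are not limited to"; none of the ten is calendar time, season or discharge date.

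On timing, the Protocol (Intervention and Interactions) says "Patient enrollment for Phase 1 of the trial will run from June 2016 to March 2018" and "Patient enrollment for Phase 2 of the trial will run from November 2017 January 2019". It adds that "there is some overlap between Phases 1 and 2", because hospitals recruited at different speeds. Exploratory Aims 3 and 4 of the Protocol describe the same before-after contrast and add no control for time.

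**The concern.** Within the former usual-care hospitals, phase and treatment are the same variable. Anything else that moved over the same period, such as coding, referral practice, payer rules or background readmission rates, goes into the phase coefficient along with COMPASS. Neither supplied document plans a trend term, an interrupted time series, a stepped-wedge model or a two-arm comparison of changes that would separate them.

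At stake is the reading of a result that the SAP files under comparative effectiveness. A favourable phase odds or hazard ratio could be partly or wholly secular, and an unfavourable trend could hide a real effect. The other arm's hospitals have claims in both phases, so a check is available on data already to be held.

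**Working it through.** The plan gives no sample size, power or effect size for this analysis, so there is no figure of its own to reproduce.

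**1. Gap between windows** (trial-wide dates from the Protocol)

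- Phase 1: 1 June 2016 to 31 March 2018, 668 days, midpoint 1 May 2017.
- Phase 2: 1 November 2017 to 31 January 2019, 456 days, midpoint 17 June 2018.
- Gap: 412 days = 412/365.25 = 1.13 years, about 13.5 months. The windows overlap by about 5 months.

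**2. What each contrast estimates**

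Let b be the log odds ratio for COMPASS, t the secular change in log odds between phases, and s the fraction of the effect kept by the Sustain hospitals.

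- Pre-post change in former usual-care hospitals: b + t.
- Sustainability change in former intervention hospitals: (s - 1)b + t.
- Pre-post minus Sustainability: (2 - s)b, if t is the same in both arms.

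The first line needs no assumption about the size of t. In the third line t cancels, and the result is zero whenever b = 0, whatever s is. If b is not zero and s is below 1, the difference exceeds b in size.

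**3. Illustrative bias and type I error with b = 0**

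Assumed: a constant yearly fall in odds; 20% risk; n patients per phase; no clustering. Then t = 1.13 x ln(1 - yearly fall), SE = sqrt(2/(n x 0.2 x 0.8)), and the two-sided 5% rejection probability is Phi(|t|/SE - 1.96) + Phi(-|t|/SE - 1.96). The SE is 0.125 at n = 800 and 0.102 at n = 1,200.

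| Assumed yearly fall in odds | t | Expected OR | Type I error, n = 800 to 1,200 |
|---|---|---|---|
| 3% | -0.034 | 0.97 | about 6% |
| 5% | -0.058 | 0.94 | about 7.5-9% |
| 8% | -0.094 | 0.91 | about 12-15% |

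The result depends on the assumed n. At a 5% yearly fall, 200 to 300 patients per phase in an insurer stratum gives about 6%. With a 25% event rate (the 90-day readmission figure in the Protocol Background) and 3,000 patients per phase, it gives about 16%.

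**4. Simulation of the two contrasts**

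Assumed: 20 hospitals per arm, 75 patients per hospital and phase, 25% baseline rate, yearly odds ratio 0.90 for the trend.

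| True OR | Fraction sustained | Pre-post OR | Two-arm OR |
|---|---|---|---|
| 1.00 | - | 0.89 | 1.00 |
| 0.85 | all | 0.76 | 0.85 |
| 0.85 | half | 0.75 | 0.78 |
| 0.85 | none | 0.75 | 0.72 |

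The two-arm values match the algebra: 0.85^1.5 = 0.78 and 0.85^2 = 0.72. The standard error of the log odds ratio rises from about 0.09 to about 0.12.

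**The case against.** The analysis is called pre-post and sits under the Protocol's Exploratory Aims. Effectiveness on the same endpoints is tested by the randomized Phase 1 comparison (SAP Section 5.1). That stands: it limits the weight of the point, but the label does not remove the bias.

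A reader might infer that the former intervention hospitals' data go unused. The documents do not support that. Those hospitals' change between phases is a planned Sustainability result with the same endpoints, strata and covariates, so a reader could nearly form the difference by hand. What is missing is a plan to form it, with an interval and its assumptions stated.

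The strongest objection concerns the remedy. The Sustain hospitals are treated in both phases and continue in Phase 2 on their own resources, and the Protocol treats persistence of effect as an open question. If the effect wanes, the two-arm estimate overstates benefit: half-waning of a true OR of 0.85 biases the log odds ratio by 0.5 x ln(0.85) = -0.081, as much as a secular fall of about 7% a year. This stands for effect size. It does not apply when COMPASS has no effect, since nothing can then wane, and that is the case in which a trend would be mistaken for benefit.

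It is also tempting to require that the two estimates agree before effectiveness is claimed. With a true OR of 0.85, a 5% yearly fall and half-waning, pre-post gives 0.85 x 0.944 = 0.80 and the two-arm estimate gives 0.78: they agree and both overstate. Disagreement could equally be noise from the wider interval.

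Finally, the open wording of Section 6.1.1 would permit a time covariate, and the Phase 1 SAP, to which this SAP is an addendum, was not supplied. The addendum cites it for study design and missing data, not for time adjustment in Phase 2.

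**Conclusion.** The point holds in a limited form. As specified, the Phase 2 pre-post estimate is the intervention effect plus any secular change, and no planned analysis separates the two. This follows from the design.

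How much it matters is not known. The trend, its direction and the linked sample sizes are not in the documents. The odds ratios of 0.97, 0.94 and 0.91 and the type I errors of about 6%, 7.5-9% and 12-15% are illustrations under assumed falling trends with clustering ignored. A rising trend would bias the other way. The 13.5-month gap uses trial-wide dates and implies even accrual; the gap within the usual-care hospitals is not documented.

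A reader might go further and conclude that the trial's evidence on effectiveness is compromised, or that the Phase 2 result must favour COMPASS. Neither follows: the randomized Phase 1 comparison is untouched, the Phase 2 analysis is exploratory, and nothing in the documents shows which way outcomes were moving.

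**What to change.** For each Phase 2 pre-post endpoint and insurer stratum, add a supplementary model over both original arms and both phases, with phase, arm and phase-by-arm terms, the Section 6.1 covariates and the clustering method already planned for that endpoint type. Code it so that the reported term is the usual-care hospitals' change minus the intervention hospitals' change. With two periods this is the same model as one with treatment, arm and period terms; finer calendar periods would also use the overlap and the differing hospital start dates. Report the estimate and interval beside the pre-post result.

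State in the SAP that:

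- the simple pre-post estimate is confounded with time;
- the two-arm estimate assumes parallel trends, which the original randomization supports but the Phase 2 delivery conditions in Section 5.2 weaken;
- for the size of a non-null effect it also assumes no waning in the Sustain hospitals, and waning would overstate benefit, so it should be read with the Sustainability result;
- agreement between the two estimates is not a formal condition for any claim.

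The cost is one extra model per endpoint and stratum on data already to be held, and a wider interval (standard error of the log odds ratio about 0.12 against 0.09 in the simulation).
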